1. INTRODUCTION

This statistical analysis plan (SAP) provides a technical and detailed elaboration of the statistical analyses of efficacy, safety, and pharmacokinetic/pharmacodynamic data as described in the study protocol Amendment 3 dated 03 February 2022. Specifications for tables, figures, and listings are contained in a separate document.

There are two parts of this study: Part A includes an approximate 8-week screening period to be followed by a 52-week main period, during which time Group 1 will have pegcetacoplan administration for all 52 weeks and Group 2 will receive pegcetacoplan administration only following the Week 12 biopsy through the remainder of the main period. All subjects then enter the 8-week follow-up period or the long-term extension (Part B).

The total duration of participation is up to 68 weeks (not including the Part B long-term extension).

For analysis purposes, data will be summarized by treatment groups and overall. When applicable (and it will be specified in the following sections), the summary tables will be further separated by the 3 treatment phases (Part A Controlled Portion, Part A Noncontrolled portion, and Part B long-term extension) and combined.

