3.5. Analysis Timing

The analysis of data from the Part A Controlled Portion of the study will be performed when all subjects have completed the Part A Controlled Portion or discontinued early and all corresponding data have been entered into the database, reviewed, cleaned, and finalized, and the Week 12 Analysis database locked. At that time, the primary analysis will be performed, which will include all efficacy and safety analyses for the Part A Controlled Portion. For Week 12 Analysis, all summary tables will be presented by randomized group.

The analysis of data from the Part A Non-Controlled Portion will be performed once all subjects have completed the Part A Non-Controlled Portion or discontinued early and all corresponding data have been entered into the database, reviewed, cleaned, and finalized, and the Week 52 Analysis database locked. For disposition, baseline summary, and efficacy analysis, tables will be presented similarly as Week 12 Analysis.

The table summaries for protocol deviations, concomitant medications, study drug exposure and compliance, as well as all AE summaries will be presented in 5 columns: (1) Group 1's Part A Controlled Portion results; (2) Group 1's Part A Non-Controlled Portion results; (3) Group 2's Part A Non-Controlled Portion results; (4) Part A Non-Controlled Portion results combined (in other words, combining columns 2 and 3); (5) for all results since Pegcetacoplan injection (in other words, combining columns 1 and 4). More details on the summary layout are provided in the separate table shell document.

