ALT or AST > 3xULN and concurrent elevated total bilirubin defined as	> 2.0xULN

For the following serum chemistry parameters: Creatinine; estimated Glomerular Filtration Rate (using CKD-EPI formula) –screening only; Albumin; LDH; Creatine kinase (CK); Uric acid; Glucose; Sodium; Potassium; and Chloride, abnormal values will be used as potentially clinically significant.

Similarly, for Urinalysis parameters, Protein; Glucose; Blood; Nitrite; and Leukocyte esterase, abnormal values will be used as potentially clinically significant.

The number and percentage of subjects with post-baseline PCS laboratory values will be tabulated by treatment group and overall. A listing of subject data with at least one post-baseline PCS value will be provided.

All laboratory values will be listed for each subject.

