7.3. Vital Signs

Observed and change from baseline in vital signs (pulse rate, respiratory rate, systolic and diastolic blood pressure, temperature, and weight) will be summarized by treatment group and overall at each analysis visit.

Additionally, the number and percentage of subjects with post-baseline potentially clinically significant (PCS) vital sign values will be tabulated. Vital signs are potentially clinically significant (PCS) if they meet the PCS criteria listed in the table below:

Table 2: Criteria for Potentially Clinically Significant Vital Signs

VS parameter	Criteria
HR	≥100 BPM <40 BPM
SBP	≥130 mm Hg ≥160 mm Hg ≥ 180 mm Hg ≥20 mm Hg increase from baseline <90 mm Hg ≥20 mm Hg decrease from baseline
DBP	≥90 mm Hg ≥15 mm Hg increase from baseline <40 mm Hg post-baseline ≥15 mm Hg decrease from baseline
Temp	≥ 38°C

All vital sign values and change from baseline values will be listed. In the listing, potentially clinically significant vital sign values will be flagged.

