7.4. Electrocardiograms (ECGs)

Observed and change from baseline in ECGs (Heart Rate, PR interval, QRS duration, QT interval, and QTc interval which is corrected by Friderica’s method) will be summarized by treatment group and overall at each analysis visit.

Additionally, the number and percentage of subjects with post-baseline potentially clinically significant (PCS) ECG values will be tabulated. ECGs are potentially clinically significant (PCS) if they meet the PCS criteria listed in the table below:

Table 3: Criteria for Potentially Clinically Significant ECGs

ECG parameter	Criteria
HR	< 40 bpm > 100 bpm
PR	> 200 msec
QRS	> 120 msec
QTcF	> 450 msec > 480 msec > 500 msec
QTcF increase from baseline	> 30 msec > 60 msec

All ECG values and change from baseline values will be listed. In the listing, potentially clinically significant ECG values will be flagged.

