13.3. Definition of Baseline

For all evaluations unless otherwise noted, baseline is defined as the most recent non- missing measurement prior to the first administration of study drug (Study Day 1 for treatment group 1), or prior to/on the randomization date (Study Day 1 for treatment group 2). Baseline can be the same date as first dose, given the measurement is expected prior to first dose when only date information is available.

In by-visit summary tables, the baseline will be summarized using all available data, but also for each visit using only the baseline data from subjects with available data at the visit; hence the mean change from baseline will equal the mean visit value – mean baseline value.

Throughout this document ‘change from baseline’ refers to the actual change from baseline (i.e. visit value – baseline value).

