13.5. Repeated or Unscheduled Assessments of Safety Parameters

For safety parameters, if a subject has repeated assessments before the start of investigational product, then the results from the final assessment made prior to the start of investigational product will be used as baseline. If end of study assessments are repeated or unscheduled, the last post-baseline assessment will be used as the end of study assessment for generating descriptive statistics. However, all post-baseline assessments will be used for Potentially Clinically Significant (PCS) value determination and all assessments will be presented in the data listings.

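### At Week 52 the ever-PCS laboratory, vital-sign and ECG tables pool Group 2's untreated and on-drug values, so neither the Group 2 nor the overall column is an on-pegcetacoplan rate

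*SAP*

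**What the plan says.** **Layout.** For laboratory values SAP 7.2 states: "The number and percentage of subjects with post-baseline PCS laboratory values will be tabulated by treatment group and overall". SAP 7.3 says that "the number and percentage of subjects with post-baseline potentially clinically significant (PCS) vital sign values will be tabulated", and SAP 7.4 that "the number and percentage of subjects with post-baseline potentially clinically significant (PCS) ECG values will be tabulated". Neither of these two names columns, so the SAP 1 default of treatment group and overall applies. SAP 1 makes any split by phase depend on a later instruction: "When applicable (and it will be specified in the following sections), the summary tables will be further separated by the 3 treatment phases". Sections 7.2 to 7.4 contain no such instruction for the PCS tables.

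**Week 52.** SAP 3.5 does give an instruction for other tables: "The table summaries for protocol deviations, concomitant medications, study drug exposure and compliance, as well as all AE summaries will be presented in 5 columns". The fifth column gathers everything since the first pegcetacoplan dose, and Group 2's untreated portion is in none of the five. Disposition, baseline and efficacy tables keep the Week 12 layout. Laboratory, vital-sign and ECG tables are in neither list.

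**What is counted.** Under SAP 13.5, "all post-baseline assessments will be used for Potentially Clinically Significant (PCS) value determination". SAP 13.3 places Group 2's baseline at randomization (Study Day 1). SAP 4.3 puts everyone randomized to Group 2 in the safety set, dosed or not. SAP 3.1 and Protocol 6.2 hold Group 2's first dose until after the biopsy due between Weeks 12 and 14.

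**The concern.** A PCS table counts a subject once if any post-baseline value crosses a threshold. If the rules above are followed at Week 52, a Group 2 subject whose only flagged value came before any drug is counted exactly like one flagged on drug, and that count also enters the overall column.

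Untreated flags are plausible. The criteria include systolic pressure of 130 mm Hg or more (SAP Table 2) and any abnormal creatinine, urine protein or urine blood (SAP 7.2). Protocol 4.1 lists proteinuria, hematuria, hypertension and reduced filtration as common manifestations of the disease itself.

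The clearest problem is inconsistency between two safety outputs of the same analysis. An abnormality recorded as an AE is placed by exposure, while the same value in the PCS table is not. Safety on pegcetacoplan is a secondary objective (SAP 2.1.2), so a reader will look to these tables for an on-drug rate.

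**Working it through.** The plan gives no figure to reproduce: sample size is not power-based and no PCS rate is stated. The steps below size the effect.

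**Inputs from the documents**
- Group sizes: 12 × 3/4 = 9 and 12 × 1/4 = 3, matching the stated maxima.
- Scheduled post-baseline main-period visits with laboratory, vital-sign and ECG assessments (Protocol Table 1): Weeks 2, 4, 8, 12, 14, 16, 20, 24, 30, 36, 42, 48, 52, which makes 13.
- Group 2 visits sampled before first dose: Weeks 2, 4, 8 and 12 if dosing starts at Visit 7; Week 14 as well if it starts at Visit 8 (Protocol 9.2.3 puts sampling before dosing).

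**Share of Group 2 follow-up that is untreated**
- Visits: 4/13 = 31% or 5/13 = 38%.
- Time: 12/52 = 23% or 14/52 = 27%.
- Planned main-period person-weeks, both groups: (3 × 12)/(12 × 52) = 5.8% or (3 × 14)/(12 × 52) = 6.7%.

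**Assumption.** Each visit carries the same independent probability p of a PCS value, with no drug effect. The documents give no p, so 2%, 5% and 10% are shown. The chance of at least one flag in n visits is 1 − (1 − p)^n.

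| p | Pooled, 13 visits | On drug, 9 visits | On drug, 8 visits |
|---|---|---|---|
| 2% | 23.1% | 16.6% | 14.9% |
| 5% | 48.7% | 37.0% | 33.7% |
| 10% | 74.6% | 61.3% | 57.0% |

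**Effect on the overall column.** Group 2 is 3 of 12 subjects, so the shift is (3/12) × (pooled − on drug).
- 9 on-drug visits: 0.25 × 6.5 = 1.6 points; 0.25 × 11.7 = 2.9; 0.25 × 13.3 = 3.3.
- 8 on-drug visits: 0.25 × 8.2 = 2.0 points; 0.25 × 15.0 = 3.8; 0.25 × 17.6 = 4.4.

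**Effect in one realized table.** Each Group 2 subject flagged only while untreated adds 1/12 = 8.3 points to the overall rate, with a ceiling of 3/12 = 25 points. The probability q of being flagged only while untreated is the pooled minus the on-drug column. The chance that at least one of three subjects is such a case is 1 − (1 − q)^3: 18%, 31% and 35% with 4 untreated visits, and 23%, 39% and 44% with 5.

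**Check on the between-group comparison.** Under the same model Group 1 also has 13 visits, so at p = 5% the planned table shows 48.7% against 48.7%, the correct null. On-drug columns alone would show 48.7% against 37.0% with no drug effect, purely because the number of visits differs. Any fix must therefore display follow-up.

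**The case against.** Several points on the other side stand.

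- **Week 12 analysis.** SAP 3.5 plans a separate controlled-portion analysis by randomized group, so Group 2's untreated PCS counts appear alone there. This does not yield its on-drug count by subtraction, because one subject can be flagged in both periods.
- **Liver.** A reader might infer that on-drug liver signals are hidden. They are not: SAP 7.2 also tabulates four ALT/AST threshold categories at each analysis visit, so Group 2's early visits are separate from the later ones.
- **Listings and AEs.** Listings show PCS values by subject and visit, and Group 2 has at most three subjects, so the split can be rebuilt by hand. Laboratory and confirmed vital-sign findings judged clinically significant also become AEs (Protocol 10.13 and 10.3), which do get exposure columns. That judgement is not the same as crossing a PCS threshold.
- **Unseen shells.** SAP 1 and 3.5 defer layout detail to separate documents, which may add columns. The Week 52 layout here follows from the SAP 1 default, and for vital signs and ECGs from that default alone.
- **Persistence.** Independence between visits is generous to the concern. If a subject flagged before drug is flagged on drug as well, the shift for that subject is zero.
- **Baseline wording.** SAP 13.5 takes the last repeated assessment before investigational product as baseline. Applied literally to Group 2, this would move its untreated weeks before baseline. But SAP 13.3 names Group 2 and uses randomization, and the literal reading would leave Group 2 no post-baseline safety data for the Week 12 analysis that SAP 3.5 requires. The ambiguity is worth closing.

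A reader might also infer that pooling pulls the comparison between groups toward zero. The documents do not support this as a finding: no Week 52 treated-versus-control safety contrast or test is planned, and the planned table is null-consistent when the drug has no effect.

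**Conclusion.** The point holds as one of table definition and consistency. Followed as written, the Week 52 ever-PCS tables mix Group 2's 12 to 14 untreated weeks with its on-drug weeks, and neither the Group 2 nor the overall column can be read as a rate on pegcetacoplan. The AE tables at the same analysis avoid this.

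The size is modest. At most 3 of 12 subjects are involved, and the expected inflation of the overall rate is about 1.6 to 3.3 points with 9 on-drug visits, or 2.0 to 4.4 with 8. This rests on an assumed 2% to 10% independent chance per visit, no drug effect, full enrollment and scheduled main-period visits only. Persistence lowers it. A single realized table can move by 8.3 points per affected subject. No efficacy conclusion is touched, and the information is recoverable elsewhere with effort. The change is worth making because it is cheap and puts an on-drug safety rate in the table where readers will look for it.

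**What to change.** In SAP 3.5 and 7.2 to 7.4, for the Week 52 PCS tables:

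1. Use the SAP 3.5 exposure columns, including the one for all results since the first pegcetacoplan dose, and add a column for Group 2's untreated controlled portion.
2. Assign each Group 2 value by its date relative to that subject's first dose, using predose or postdose order on the day itself. Visit windows alone would misplace a predose Week 14 sample, because SAP 13.4 puts that window in the noncontrolled portion.
3. Show the number of visits or the exposure time per column, and base on-drug denominators on subjects who were dosed.
4. If an overall column is kept, label it as mixed exposure. Removing it is a matter of preference and is not needed.
5. State that SAP 13.3 governs Group 2's baseline for the PCS tables, so that SAP 13.5 cannot be read otherwise.

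The cost is SAP wording, revised shells and a few more columns. It uses data already collected and changes nothing in trial conduct.

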7.3. Vital Signs

Observed and change from baseline in vital signs (pulse rate, respiratory rate, systolic and diastolic blood pressure, temperature, and weight) will be summarized by treatment group and overall at each analysis visit.

Additionally, the number and percentage of subjects with post-baseline potentially clinically significant (PCS) vital sign values will be tabulated. Vital signs are potentially clinically significant (PCS) if they meet the PCS criteria listed in the table below:

Table 2: Criteria for Potentially Clinically Significant Vital Signs

VS parameter	Criteria
HR	≥100 BPM <40 BPM
SBP	≥130 mm Hg ≥160 mm Hg ≥ 180 mm Hg ≥20 mm Hg increase from baseline <90 mm Hg ≥20 mm Hg decrease from baseline
DBP	≥90 mm Hg ≥15 mm Hg increase from baseline <40 mm Hg post-baseline ≥15 mm Hg decrease from baseline
Temp	≥ 38°C

All vital sign values and change from baseline values will be listed. In the listing, potentially clinically significant vital sign values will be flagged.

7.4. Electrocardiograms (ECGs)

Observed and change from baseline in ECGs (Heart Rate, PR interval, QRS duration, QT interval, and QTc interval which is corrected by Friderica’s method) will be summarized by treatment group and overall at each analysis visit.

Additionally, the number and percentage of subjects with post-baseline potentially clinically significant (PCS) ECG values will be tabulated. ECGs are potentially clinically significant (PCS) if they meet the PCS criteria listed in the table below:

Table 3: Criteria for Potentially Clinically Significant ECGs

ECG parameter	Criteria
HR	< 40 bpm > 100 bpm
PR	> 200 msec
QRS	> 120 msec
QTcF	> 450 msec > 480 msec > 500 msec
QTcF increase from baseline	> 30 msec > 60 msec

All ECG values and change from baseline values will be listed. In the listing, potentially clinically significant ECG values will be flagged.

7.5. Other Safety Data

Physical examinations will be described in a data listing.

8. PHARMACOKINETIC ANALYSIS

8.1. Drug Concentration

Individual pegcetacoplan concentrations, actual sampling times and deviations from nominal sampling times will be presented in a data listing for all subjects included in the PK Population.

Pegcetacoplan concentrations will be summarized by treatment group at each scheduled time point using descriptive statistics (including mean, SD, coefficient of variation (CV), Median, Min, Max, Geometric Mean/%CV). The number of subjects with a below the limit of quantification (BLQ) concentration at each scheduled time point will also be tabulated. The handling of BLQ concentrations in the summary tables is described in Section 8.2. Missing values will be omitted from the calculation of descriptive statistics.

Linear and semilogarithmic individual concentration-time profiles will be generated using actual sampling times. Linear and semilogarithmic mean (\pm SE) and median concentration-time profiles will be generated using nominal sampling times. The number of subjects contributing to each mean or median value at a visit will be presented above the x-axis.

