Urine pregnancy test		X	X	X	X	X	X	X	X	X	X	X	X	X	X	X	X	X	X
FSH, HIV, HCV, HBsAg, HBcAb R	х																		
AEs	Х	X	х	Х	Х	Х	X	X	Х	Х	Х	X	Х	X	X	X	X	X	X
Post-transplant immunosuppression plan documentation		x																	
Ophthalmologic evaluation (optional) S		XS													XS				

Abbreviations: ADA = antidrug antibodies; AE = adverse events;  $\beta$ -HCG =  $\beta$ -human chorionic gonadotropin; CDC = Centers for Disease Control and Prevention;

NOTE: When multiple assessments/procedures occur at the same time, order should be: vital signs, ECGs, blood collection/sampling, pegcetacoplan dosing.

CKD-EPI = Chronic Kidney Disease-Epidemiology Collaboration; ECG = electrocardiogram; eGFR = estimated glomerular filtration rate;

FSH = follicle-stimulating hormone; GFR = glomerular filtration rate; HBcAb = hepatitis B core antibody; HBsAg = hepatitis B surface antigen;

HCV = hepatitis C; N/A = not applicable; PK = pharmacokinetic(s); RBC = red blood cell; SC = subcutaneous;

SD-OCT = spectral domain optical coherence tomography.

A. Subjects who meet the medical history requirements will enter the screening period at Visit 1 and return for Visit 2, but all Visit 2 assessments need not occur in a single visit and Visit 2 can be split into multiple visits (eg, 2a, 2b).

- B. Subjects will self-administer SC pegcetacoplan after receiving appropriate training and sign-off by a research nurse or other personnel in their first treatment week. During site visits subjects will self-administer pegcetacoplan at the site, with the exception of the very first dose. Group 2 subjects will be trained on self-administration of pegcetacoplan and receive their supply of pegcetacoplan at the next scheduled clinic visit (Visit 7 or 8) following their biopsies.
- C. Visit 2 must occur at least 7 days after Visit 1 and at least 14 days prior to the Day 1 dosing date; the vaccinations and biopsy can occur any time after confirmation of eligibility based on Visit 1 data.
- D. Specific inclusion/exclusion criteria will be measured during screening, and some of them require confirmation prior to any activities of Day 1. See the inclusion/exclusion criteria in Section 7 for further detail.

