#### 12.2.5. PD Set

The PD set will include all subjects in the ITT set who receive pegcetacoplan and have at least 1 evaluable postdose PD measurement.

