4.5. Pharmacodynamic Set

The PD set includes all subjects in the ITT set who had at least 1 evaluable postscreening PD measurement.

All PD analyses will be conducted using the PD set.

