9. PHARMACODYNAMIC ANALYSIS

9.1. Pharmacodynamic Data

Observed values, changes from baseline and percentage changes from baseline in C3, AH50, CH50, C3b/iC3b, sC5b9, C4, and C3a will be summarized at each protocol specified time point using descriptive statistics.

Individual observed values and individual changes from baseline will be presented graphically. Actual sampling times will be used for the graphical presentation of individual data. The mean (\pm SE) of the observed values, mean changes from baseline, and mean percentage changes from baseline will also be presented graphically. Nominal sampling times will be used for the mean plots.

PD parameters will be listed together with changes from baseline and percentage changes from baseline by treatment group.

In addition to the analyses outlined above, all PK and complement biomarker (PD) concentration data may be used to develop the population PK and exposure-response models in conjunction with other clinical study data. The methods and procedures will be described in a separate Analysis Plan if needed. The results from population modeling will be reported separately.

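### Group 2 starts drug at Week 12 or Week 14, but the SAP ties its PK/PD time axis, PD baseline and BLQ rule to Day 1 and its on-drug safety column to calendar weeks

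*SAP*

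**What the plan says.** **First dose in Group 2.** Under Protocol Section 9 (Table 1, footnote B), Group 2 subjects are trained and "receive their supply of pegcetacoplan at the next scheduled clinic visit (Visit 7 or 8) following their biopsies". Table 1 places these visits at Days 84 and 98. The biopsy may fall anywhere from Week 12 to Week 14.

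**Time axis.** SAP 13.2 counts study days from Study Day 1 in both groups. SAP 8.1 states: "Pegcetacoplan concentrations will be summarized by treatment group at each scheduled time point using descriptive statistics". SAP 9.1 states that observed values, changes and percentage changes in the complement markers "will be summarized at each protocol specified time point using descriptive statistics". It does not say whether these summaries are by group; only the listing is.

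**Baseline.** SAP 13.3 takes the last value before first dose in Group 1, "or prior to/on the randomization date (Study Day 1 for treatment group 2").

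**BLQ rule.** SAP 8.2.1 and 8.2.2 treat BLQ values differently before and after first dosing, and identify first dosing with Day 1.

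**Five-column layout.** SAP 3.5 applies it to deviations, concomitant medications, exposure, compliance and AEs. Column 3 is Group 2's Non-Controlled Portion, which SAP 3 gives as Weeks 13-52. Column 4 adds Group 1's, and the last column is "5) for all results since Pegcetacoplan injection (in other words, combining columns 1 and 4").

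**Default columns.** SAP 1 states: "For analysis purposes, data will be summarized by treatment groups and overall". Tables are split by treatment phase only where a section says so; Sections 8 and 9 do not.

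**PD set.** Protocol 12.2.5: "The PD set will include all subjects in the ITT set who receive pegcetacoplan and have at least 1 evaluable postdose PD measurement". SAP 4.5: "The PD set includes all subjects in the ITT set who had at least 1 evaluable postscreening PD measurement". SAP 15 reports no changes from the protocol.

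**The concern.** For Group 1, randomization and first dose coincide, so a Day 1 clock serves both. For Group 2 they are 12 to 14 weeks apart, and the gap differs between subjects. A table indexed by study week then does not show time on drug for Group 2, and a change from Day 1 includes a long untreated stretch. Protocol 8.8 lets anticipated post-transplant immunosuppression adjustments go ahead during that stretch, so the off-drug value need not stay still.

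Concentration over time and change in CH50 and AH50 over time are the protocol's stated PK and PD endpoints (Protocol 5.2.3 and 5.2.4). The crossover in Group 2 is the one place where the same subject is seen off and then on drug.

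The column in SAP 3.5 raises a labelling question. SAP 7.1 counts Group 2 AEs as treatment-emergent from randomization. An event after the Week 12 biopsy but before a Visit 8 first dose would therefore qualify as a TEAE, fall in the Non-Controlled Portion, and be reported under a heading that says the subject had been injected.

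**Working it through.** **1. Group sizes.** Up to 12 subjects at 3:1 gives 12 × 3/4 = 9 and 12 × 1/4 = 3, matching SAP 3. The 12 is not derived from power, so there is no further figure to reproduce.

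**2. Which Group 2 visits are off drug.** Protocol Table 1 has 14 main-period visits with a complement sample: Weeks 1, 2, 4, 8, 12, 14, 16, 20, 24, 30, 36, 42, 48, 52. The sample at the dosing visit is taken before the dose.

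| First dose | Off-drug PD visits | On-drug PD visits | Weeks on drug at the on-drug visits |
|---|---|---|---|
| Week 12 | 5 | 9 | 2, 4, 8, 12, 18, 24, 30, 36, 40 |
| Week 14 | 6 | 8 | 2, 6, 10, 16, 22, 28, 34, 38 |

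Off-drug and on-drug samples can share a row only at Week 14, where 0 to 3 of 3 Group 2 subjects may be on drug. This holds for PK too: Table 1 footnote N limits controlled-period PK sampling to Group 1. (Protocol 9.2.3.1 and 12.5 imply Group 2 PK from Week 12. These passages need reconciling.)

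**3. Week 14 PK.** If one of three Group 2 subjects is pre-dose and entered as zero, and the other two have concentration c, the mean is 2c/3, one third below the dosed subjects' mean. Under SAP 8.2.1 the pre-dose BLQ value is zero if first dosing means the subject's own first dose, and LLOQ/2 if it means Day 1. With a zero, no geometric mean can be calculated.

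**4. Week 16.** Days on drug are 112 − 84 = 28 or 112 − 98 = 14. The Amendment 3 summary of changes gives an effective half-life of 8 to 10 days. Assuming linear accumulation, the fraction of steady state is 1 − 2^(−t/T):
- 14 days: 0.70 (T = 8), 0.62 (T = 10)
- 28 days: 0.91 (T = 8), 0.86 (T = 10)

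**5. PD baseline.** From Day 1 to first dose is 84 − 1 = 83 or 98 − 1 = 97 days, about 12 to 14 weeks. If U is the change over that untreated time and E the change after first dose, the planned Group 2 figure is U + E. It equals E only when U = 0. The documents give no value for U.

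**6. SAP 3.5 column.** Twelve weeks end on Day 84, so Weeks 13-52 begin on Day 85. A Day 98 starter is undosed on Days 85 to 97, which is 98 − 85 = 13 days. With Visit 8's ±7-day window (Days 91 to 105) this is 6 to 20 days. Treatment duration in SAP 5.5 already runs from the first infusion, so within this layout the AE, concomitant medication and deviation counts are the most exposed. Compliance depends on how expected infusions are counted.

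**7. Pooled PD column, if one is produced.** With change D in Group 1 and none in Group 2, a pooled mean at Weeks 2-12 is (9D + 3 × 0)/12 = 0.75D. With 6 to 9 evaluable subjects in Group 1 and 2 or 3 in Group 2, the factor runs from 6/9 = 0.67 to 9/11 = 0.82.

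**The case against.** Much can fairly be said for the plan. The study is descriptive and Group 2 has at most 3 subjects. Individual PK and PD profiles are plotted on actual sampling times, and the PK listing gives actual times, so onset in Group 2 can be seen subject by subject. A Day 1 baseline is right for the randomized comparison to Week 12. The 75% figure assumes controls do not change, and under that same assumption the choice of baseline makes no difference. Re-indexing is also awkward: of a Week 14 starter's on-drug visits, only 2 and 16 weeks coincide with Group 1's visits.

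All of this stands and limits the point. It also rules out four stronger readings that a reader might infer:

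- *Group 2's PK and PD tables mix off-drug and on-drug samples throughout.* They are by visit, so this is confined to Week 14. SAP 8.1 has no change-from-baseline PK summary, so the Day 1 baseline concerns PD only.
- *The PD means will be diluted by 25%.* SAP 9.1 names no overall column. It would arise only from the general sentence in SAP 1, and SAP 3.5 presents the Week 12 analysis by randomized group.
- *The altered PD set is what admits untreated Group 2 values.* Both definitions select subjects, not visits. A Group 2 subject who is later dosed and has a post-dose value is in either set, with the untreated visits included.
- *The SAP 3.5 column distorts PK and PD.* That layout does not cover them.

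These points do not supply a first-dose clock, a pre-dose PD baseline for Group 2, an unambiguous BLQ rule, or a correct start for the since-injection column.

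**Conclusion.** The concern holds in limited form. The firmest part is SAP 3.5: read with SAP 3, it places about 13 undosed days (6 to 20 within the visit window) of a Visit 8 starter under an on-drug label, at a time when a biopsy has usually just been taken. This assumes the portion is cut by calendar week as SAP 3 describes. The table shells, which are a separate document, might define it otherwise.

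For PK and PD, the gap is the absence of any summary by time since first dose and of any Group 2 PD change from a pre-dose value. Its visible effects are one possibly mixed row at Week 14 and unequal time on drug at Week 16 (62-70% versus 86-91% of steady state, assuming linear accumulation and the stated half-life). The size of any baseline bias cannot be given from the documents. The 75% pooled figure is conditional on a pooled column being produced, full 9:3 enrolment and no change in controls. The PD-set change is real and undeclared, but it is a separate matter of record.

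**What to change.** 1. **SAP 3.5:** start Group 2's contribution to the since-injection column at each subject's actual first-dose date.
2. **SAP 9.1:** state that PD is summarised by randomized group, with no pooled column before Group 2 is dosed. Keep Day 1 as baseline for the randomized comparison to Week 12. Add a Group 2 on-drug PD summary that uses the last value before the subject's own first dose as baseline.
3. **SAP 8.1 and 9.1:** show Group 2's on-drug PK and PD by time since first dose, as individual profiles or in broad windows, since exact matching to Group 1's visits would leave rows of one or two subjects. Exclude or flag pre-dose samples at Week 14.
4. **SAP 8.2:** define the period before first dosing by each subject's own first dose and remove the equation with Day 1.
5. **SAP 15:** declare and justify the changed PD set. This alone does not remove untreated Group 2 visits from the summaries; item 2 deals with those.

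The cost is one derived time variable, one extra small PD table and some shell edits. First-dose dates and the Visit 7 and 8 complement samples are already collected, so no new data are needed.
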